2.4.2. Part 2: Expansion Cohort

The primary goal of Part 2 is to characterize clinical activity of the combination and to detect if meaningful response rate (ORR) can be achieved. Based on historical information [[Lokhorst](#), 2015] and clinical judgement, the null hypothesis has been defined as $ORR \leq 40\%$. The alternative hypothesis has been defined as $ORR \geq 60\%$ based on clinically meaningful improvement of 20%.

In Part 2, treatment-related Grade 4 or higher AEs will be continuously monitored starting from when 5 participants are dosed. Based on the 11% Grade 4 or higher AEs observed in the FTIH study (BMA117159), it is considered that the combination treatment has unacceptable toxicity if observed treatment-related Grade 4 or higher AEs is significantly higher than 12% at 1-sided alpha of 0.025.

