3.1.2.1. Operating Characteristics of the Stopping Rules for Futility

The futility stopping rule in Table 3 is based on the methodology of Lee et al. [Lee, 2008]. The optimal design has a maximum sample size of 28 and a type I error rate of 0.10 and power of 80.6%. The expansion cohort may be stopped early for futility if the predicted probability of success is less than 1.5%. Under the null hypothesis, if the true ORR is 40%, the expected sample size of the design is 20 subjects and probability of early termination is 86.1%. Under the alternative hypothesis, if the true ORR is 60%, the expected sample size is 28 and the probability of early termination is 15.6%.

Table 3 Decision Making Criteria for Futility Analysis

Number of Evaluable Subjects	\leq This Number of Responses to Stop Early for Futility	Probability of continuing enrolling when ORR=0.4	Probability of continuing enrolling when ORR=0.6
10	2	83.3%	98.8%
11	2	83.3%	98.8%
12	3	75.5%	98.1%
13	3	75.5%	98.1%
14	4	68.6%	97.5%
15	4	68.6%	97.5%
16	5	62.3%	96.9%
17	6	52.9%	95.7%
18	6	52.9%	95.7%
19	7	46.7%	94.9%
20	7	46.7%	94.9%
21	8	41.6%	94.2%
22	9	34.6%	92.8%
23	9	34.6%	92.8%
24	10	30.2%	91.9%
25	11	24.4%	90.2%
26	12	18.8%	87.7%
27	13	13.9%	84.5%
28	14	0.0%	0.0%

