16.11.5. Efficacy Tables

Efficacy: Tables					
No.	Population	IDSL / Example Shell	Title	Programming Notes	Deliverable [Priority]
Responses.					
2.001	All Treated	RE1a	Summary of Investigator Assessed Best Response (With Confirmation) (IMWG 2016)	
Report for: Part 1, Part 2, and combined Part 1 and Part 2; Summarize by: dose level (Refer to Section 5.1 for ordering of dose level and omit 1.92 mg/kg if data is not available);
 
Best Response: Stringent Complete Response (sCR), Complete response (CR), Very Good Partial Response (VGPR), Partial Response (PR), Minimal Response (MR), Stable Disease (SD), Progressive Disease (PD), Not Evaluable (NE).
 
Overall Response Rate: (sCR+CR+VGPR+PR).
 
Rate of Very Good Partial Response or better: (sCR+CR+VGPR).
 
Clinical Benefit Rate: (sCR+CR+VGPR+PR+MR).
	HDL [2], P-SAC [3], F-SAC [4]

Efficacy: Tables					
No.	Population	IDSL / Example Shell	Title	Programming Notes	Deliverable [Priority]
				
Include: Overall Response Rate, Rate of VGPR or better and Clinical Benefit Rate (include p-value for the overall response rate for part 2 P-SAC deliverable only) in one table.
 
Include the following footnotes for P-SAC and F-SAC deliverables:
 
“Note: The 95% Confidence Interval is based on Exact method.”
 
Include the following footnotes for P-SAC deliverable:
 
“(1) Probability under the null hypothesis: p=10% of an outcome at least as extreme as that observed.”
	
2.002	All Evaluable	RE1a	Summary of Investigator Assessed Best Response (for Interim Futility Analyses) (IMWG 2016)	
Report for: futility interim analyses for part 2 participants and part 1 participants who initially received the RP2D (Refer to Section 5.1 for ordering of dose level)
 
Add the following footnote: A subject is evaluable for interim analysis if the subject fulfils the criteria for ‘All Treated’ population
	IA [1]

Efficacy: Tables					
No.	Population	IDSL / Example Shell	Title	Programming Notes	Deliverable [Priority]
				with adequate baseline assessment and measurable disease meet at least one of the following criteria: if the planned assessment is every 3 weeks and at least three assessments are required, the time from the first dose to the time of data cut-off is more than 66 days, OR had an unconfirmed response of PR/CR or better, progressed, OR died, OR discontinued treatment due to other reasons.	

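### The Part 2 primary ORR table computes its p-value against a 10% null response rate, but the trial's null is 40%

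*SAP*

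**What the plan says.** Section 2.4.2 states the Part 2 hypotheses: the null is an ORR of 40% or less, the alternative an ORR of 60% or more.

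Section 3.1.2.1 gives the design on the same null: "Under the null hypothesis, if the true ORR is 40%, the expected sample size of the design is 20 subjects". It also states: "The optimal design has a maximum sample size of 28 and a type I error rate of 0.10 and power of 80.6" per cent. Table 3 lists the futility boundary from 10 to 28 evaluable subjects and ends with 14 responses at 28, so success needs at least 15.

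Section 16.11.5, Table 2.001, is the primary response table. Its programming note says to "include p-value for the overall response rate for part 2 P-SAC deliverable only". The footnote prescribed for that deliverable reads: "Probability under the null hypothesis: p=10% of an outcome at least as extreme as that observed".

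Section 7.2.1.4, on the methods for the primary efficacy analysis, names no test and no null value. It refers to descriptive statistics and to the list of displays in Appendix 11. The Table 2.001 footnote is therefore the only text that says what the primary p-value is computed against.

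**The concern.** A p-value for a response rate has meaning only relative to its null rate. The hypothesis section and the design use 40%; the table that will carry the p-value uses 10%. Both cannot stand, and the one the programmer will follow is the footnote.

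The error runs one way. For any observed count above zero, the upper-tail probability is smaller under 10% than under 40%, so the printed p-value always looks better than the correct one. A result that the design counts as failure could stand in the primary efficacy table beside a very small p-value.

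The document does not show where the 10% comes from. The only 10% in the ORR design is the type I error rate of 0.10, so a misplaced alpha is possible, as is text carried over from another study. Neither rescues the footnote, which defines a probability computed under that null.

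**Working it through.** **Inputs.** Null 40% and alternative 60% (Section 2.4.2); maximum n = 28, type I error 0.10, power 80.6%, and the boundary in Table 3 (Section 3.1.2.1); null 10% (Table 2.001 footnote).

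**Step 1: reproduce the design.** Start with no subjects and no responses. At each new subject with response probability p, update

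P(n, k) = P(n−1, k)·(1−p) + P(n−1, k−1)·p.

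From n = 10 to 27, remove as stopped every path with k at or below the Table 3 bound. At n = 28, success is k ≥ 15.

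| Quantity | SAP | Recomputed |
|---|---|---|
| Type I error, p = 0.40 | 0.10 | 0.0997 |
| Power, p = 0.60 | 80.6% | 80.55% |
| Early termination, p = 0.40 | 86.1% | 86.1% |
| Early termination, p = 0.60 | 15.6% | 15.5% |

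With p = 0.10 the same recursion gives a success probability of 1e-8. The design null is 40%, and 10% cannot be it.

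**Step 2: the printed p-value under each null.** One-sided exact p = P(X ≥ r), X ~ Binomial(28, p0).

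| Responders of 28 | Rate | p0 = 0.10 | p0 = 0.40 |
|---|---|---|---|
| 7 | 25.0% | 0.018 | 0.969 |
| 11 | 39.3% | 0.00004 | 0.601 |
| 14 (failure in Table 3) | 50.0% | 1.0e-7 | 0.187 |
| 15 (smallest success) | 53.6% | 1.0e-8 | 0.102 |
| 16 | 57.1% | 9.3e-10 | 0.050 |

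**Step 3: how often the p-value looks significant when the null is true.** Against 10% at n = 28, 5 responders give p = 0.142, 6 give 0.055 and 7 give 0.018. So p ≤ 0.10 needs at least 6, and p ≤ 0.025 needs at least 7. At a true ORR of 40%, without futility stopping:

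- P(X ≥ 6) = 98.9%
- P(X ≥ 7) = 96.9%

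**Step 4: the same with the Table 3 stops enforced.** The p-value against 10% is taken at the sample size where each path stops. At the bounds for 10 to 13 subjects it exceeds 0.10: 2/10 gives 0.264, 2/11 gives 0.303, 3/12 gives 0.111 and 3/13 gives 0.134. At a true ORR of 40%, 24.5% of trials have stopped by then (100% − 75.5%, the Table 3 continuation probability). The bounds at 14 and 15 give 0.044 and 0.056, and every bound from 5/16 onwards gives 0.017 or less. Hence at a true ORR of 40%:

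- p ≤ 0.10: 75.5%
- p ≤ 0.025: 68.6%

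**The case against.** Four points can be made against the size of this concern.

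1. **The decision rule is intact.** Table 3 fixes success at 15 of 28 or more, and Table 2.001 also prints an exact 95% confidence interval. A reader of 11/28 would see an interval that contains 40%, and the footnote shows its 10% openly. This stands: the damage is to the reported p-value and how it is read, in one deliverable.
2. **The 98.9% and 96.9% ignore futility stopping.** This stands in part. With the bounds enforced the figures are 75.5% and 68.6%. The rule is non-binding, so the truth lies between the two sets, and both are far above the design's 10%.
3. **Counts of 7 or 11 at n = 28 cannot occur if the bounds are followed,** since the smallest count that reaches 28 is 14. This holds only for the interim count. The interim uses unconfirmed responses and may include Part 1 subjects who initially received the recommended dose, while the final ORR uses confirmed responses, so a lower final count is possible. The 14/28 case needs no such argument. It is also fair that stops at 10 to 13 subjects would not print a significant p-value; the later stops from 5/16 would.
4. **Replacing only the number leaves a new mismatch.** At 15/28 the plain exact p against 40% is 0.102, just above 0.10, although the design counts 15/28 as success. This stands, and the fix below covers it.

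**Conclusion.** The concern holds. The null in the Table 2.001 footnote contradicts the null in Sections 2.4.2 and 3.1.2.1, and nothing elsewhere in the SAP supports or corrects the 10%. As written, the p-value cannot separate success from failure as the trial defines them: at a true ORR of exactly 40% it would be 0.10 or less in 75.5% of trials with the futility stops enforced and in 98.9% without them, against a design type I error of 10%.

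The p-values at n = 28 assume that all 28 subjects enter the Part 2 analysis. All figures assume a one-sided exact test; the SAP does not state the side, but the upper tail is the natural reading for a single-arm design of this kind. The futility boundary and the confidence interval are not affected. Because the error sits in the only test result specified for the primary endpoint and always favours the treatment, it must be corrected.

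**What to change.** - In footnote (1) of Table 2.001, replace the null rate of 10% with an ORR of 40%, and program the exact binomial test with p0 = 0.40.
- In Section 7.2.1.4, name the test (one-sided exact binomial, null ORR of 40% or less) and its level (0.10).
- Add one line saying that success is judged by the Table 3 boundary, at least 15 responders of 28, and that the p-value is descriptive; or else specify a p-value that accounts for the futility stops. Without this line, 15/28 would be a success printed beside p = 0.102.

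The cost is one number in a footnote, one program parameter and two sentences in Section 7.2.1.4. No data, sample size or boundary changes. The reported p-value becomes less favourable.

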16.11.6. Efficacy Figures

Efficacy: Figures					
No.	Population	IDSL / Example Shell	Title	Programming Notes	Deliverable [Priority]
Response					
2.001	All Treated	Programming Note	Forest Plot – Overall Response Rate (ORR) Based on Investigator-Assessed Response	Report for Part 1 and Part 2, and combined Part 1 and Part 2: Similar to Figure 12.012 in BMA117159 (primary_02).	P-SAC [3], F-SAC [4]
2.002	All Treated	RE8b	Investigator Assessed Maximum Percent Reduction from Baseline in M-Protein (or FLC) Measurement	Report for: Part 1, Part 2, and combined Part 1 and Part 2; Summarize by: dose level (Refer to Section 5.1 for ordering of dose level and omit 1.92 mg/kg if data is not available) Total. Refer to mid205678 (primary_01) Figure 2.0030 for guidance	P-SAC [3], F-SAC [4]
Time-to-Event Endpoints					
2.003	All Treated	TTE10	Graph of Kaplan Meier Survival Curves for Duration of Response (GSK2857916 2.5 mg/kg)	Report for: 2.5 mg/kg doses only; Refer to Section 5.1 and use only code A, code D, and code H for dose level;	P-SAC [3], F-SAC [4]
2.004	All Treated	TTE10	Graph of Kaplan Meier Survival Curves for Time to Response (GSK2857916 2.5 mg/kg)	Report for: 2.5 mg/kg doses only; Refer to Section 5.1 and use only code A, code D, and code H for dose level;	P-SAC [3], F-SAC [4]
2.005	All Treated	TTE10	Graph of Kaplan Meier Survival Curves for Time to Best Response (GSK2857916 2.5 mg/kg)	Report for: 2.5 mg/kg doses only; Refer to Section 5.1 and use only	P-SAC [3], F-SAC [4]

Efficacy: Figures					
No.	Population	IDSL / Example Shell	Title	Programming Notes	Deliverable [Priority]
				code A, code D, and code H for dose level;	
2.006	All Treated	TTE10	Graph of Kaplan Meier Survival Curves for Progression Free Survival (GSK2857916 2.5 mg/kg)	Report for: 2.5 mg/kg doses only; Refer to Section 5.1 and use only code A, code D, and code H for dose level;	P-SAC [3], F-SAC [4]
2.007	All Treated	TTE10	Graph of Kaplan Meier Survival Curves for Time to Progression (GSK2857916 2.5 mg/kg)	Report for: 2.5 mg/kg doses only; Refer to Section 5.1 and use only code A, code D, and code H for dose level;	P-SAC [3], F-SAC [4]
2.008	All Treated	TTE10	Graph of Kaplan Meier Survival Curves for Overall Survival (GSK2857916 2.5 mg/kg)	Report for: 2.5 mg/kg doses only; Refer to Section 5.1 and use only code A, code D, and code H for dose level;	P-SAC [3], F-SAC [4]

16.11.7. Safety Tables

Safety: Tables					
No.	Population	IDSL / Example Shell	Title	Programming Notes	Deliverable [Priority]
Adverse Events (AEs)					
3.001	All Treated	AE5B	Summary of All Adverse Events by System Organ Class and Preferred Term and Maximum Grade	Report for: Part 1, Part 2, and combined Part 1 and Part 2; ; Summarize by: dose level (Refer to Section 5.1 for ordering of dose level and omit 1.92 mg/kg if data is not available) Total.	P-SAC [3], F-SAC [4]
3.002	All Treated	AE5B	Summary of All Treatment-Emergent Adverse Events by System Organ Class and Preferred Term and Maximum Grade	Report for: Part 1, Part 2, and combined Part 1 and Part 2; ; Summarize by: dose level (Refer to Section 5.1 for ordering of dose level and omit 1.92 mg/kg if data is not available) Total.	P-SAC [3], F-SAC [4]
3.003	COVID-19	AE5B	Summary of All COVID-19 Adverse Events by System Organ Class and Preferred Term and Maximum Grade	Report for: Part 1, Part 2, and combined Part 1 and Part 2; ; Summarize by: dose level (Refer to Section 5.1 for ordering of dose level and omit 1.92 mg/kg if data is not available) Total. only if greater than 5 participants with COVID-19 infection; If less than 5 participants, produce listing instead;	P-SAC [3], F-SAC [4]

Safety: Tables					
No.	Population	IDSL / Example Shell	Title	Programming Notes	Deliverable [Priority]
3.004	All Treated	AE3	Summary of Common (>=5%) Adverse Events by Overall Frequency	Report for: Part 1, Part 2, and combined Part 1 and Part 2; Summarize by: dose level (Refer to Section 5.1 for ordering of dose level and omit 1.92 mg/kg if data is not available) Total.	P-SAC [3], F-SAC [4]

Safety: Tables					
No.	Population	IDSL / Example Shell	Title	Programming Notes	Deliverable [Priority]
3.005	All Treated	AE13	Adverse Event Overview	
Report for: Part 1, Part 2, and combined Part 1 and Part 2; Summarize by: dose level (Refer to Section 5.1 for ordering of dose level and omit 1.92 mg/kg if data is not available) Total. Refer to mid205678 (primary_01) Table 3.0010 for guidance. Include the following additional categories under "Any AE":
 
 • AEs leading to drug interruption and/or dose reduction; • AEs related to study treatment and lead to permanent discontinuation of study treatment • Grade 3 or 4 AEs • For the "Grade 3 or 4 AEs related to study treatment", replace with the following two subcategories: "Grade 3 or 4 AEs related to GSK2857916" and "Grade 3 or 4 AEs related to pembrolizumab" 	P-SAC [3], F-SAC [4]

Safety: Tables					
No.	Population	IDSL / Example Shell	Title	Programming Notes	Deliverable [Priority]
3.006	All Treated	See programming notes	Overview of Corneal Events (GSK Scale)	Report for: Part 1, Part 2, and combined Part 1 and Part 2; Summarize by: dose level (Refer to Section 5.1 for ordering of dose level and omit 1.92 mg/kg if data is not available) Total. Include category 'dose interruption and/or dose reduction'; Refer to mid205678 (primary_01) Table 3.0900 for guidance.	P-SAC [3], F-SAC [4]
3.007	All Treated	AE13	Overview of Eye Disorders (CTCAE)	Report for: Part 1, Part 2, and combined Part 1 and Part 2; Summarize by: dose level (Refer to Section 5.1 for ordering of dose level and omit 1.92 mg/kg if data is not available) Total. Refer to mid205678 (primary_01) Table 3.0900 for guidance. Include the following additional categories under "Any AE": 
• AEs leading to drug interruption and/or dose reduction;• AEs related to study treatment and lead to permanent discontinuation of study treatment• Grade 3 or 4 AEs	P-SAC [3], F-SAC [4]

Safety: Tables					
No.	Population	IDSL / Example Shell	Title	Programming Notes	Deliverable [Priority]
3.008	All Evaluable	AE13	Adverse Event Overview	
Report for: futility interim analyses for part 2 participants and part 1 participants who initially received the RP2D (Refer to Section 5.1 for ordering of dose level)
 
Add the following footnote: A subject is evaluable for interim analysis if the subject fulfils the criteria for 'All Treated' population with adequate baseline assessment and measurable disease meet at least one of the following criteria: if the planned assessment is every 3 weeks and at least three assessments are required, the time from the first dose to the time of data cut-off is more than 66 days, OR had an unconfirmed response of PR/CR or better, progressed, OR died, OR discontinued treatment due to other reasons
	IA [1]
3.009	All Treated	AE3	Summary of All Adverse Events by Preferred Term	
Report for: Part 1, Part 2, and combined Part 1 and Part 2; Summarize by: dose level (Refer to Section 5.1 for ordering of dose level and omit 1.92 mg/kg if data is not available) Total.
	P-SAC [3], F-SAC [4]

Safety: Tables					
No.	Population	IDSL / Example Shell	Title	Programming Notes	Deliverable [Priority]
3.0010	All Treated	AE3	Summary of Common (>=5%) Grade 2-4 Adverse Events by Overall Frequency	Report for: Part 1, Part 2, and combined Part 1 and Part 2; Summarize by: dose level (Refer to Section 5.1 for ordering of dose level and omit 1.92 mg/kg if data is not available) Total.	P-SAC [3], F-SAC [4]
3.0011	All Treated	AE5B	Summary All Drug-Related Adverse Events by System Organ Class and Preferred Term and Maximum Grade	Report for: Part 1, Part 2, and combined Part 1 and Part 2; Summarize by: dose level (Refer to Section 5.1 for ordering of dose level and omit 1.92 mg/kg if data is not available) Total.	P-SAC [3], F-SAC [4]
3.0012	All Treated	AE15	Summary of Common (>=5%) Non-serious Adverse Events by System Organ Class and Preferred Term (Number of Subjects and Occurrences)	Report for: Part 1, Part 2, and combined Part 1 and Part 2; ; Summarize by: dose level (Refer to Section 5.1 for ordering of dose level and omit 1.92 mg/kg if data is not available) Total..	P-SAC [3], F-SAC [4]
3.0013	All Treated	AE3	Summary of Common (>=5%) Drug-Related Grade 2-4 Adverse Events by Overall Frequency	Report for: Part 1, Part 2, and combined Part 1 and Part 2; Summarize by: dose level (Refer to Section 5.1 for ordering of dose level and omit 1.92 mg/kg if data is not available) Total.	P-SAC [3], F-SAC [4]
3.0014	All Treated	AE3	Summary of Non-Serious Drug-Related Adverse Events by Overall Frequency	Report for: Part 1 Part 2, and combined Part 1 and Part 2; Summarize by: dose level (Refer to Section 5.1 for ordering of dose level and omit 1.92 mg/kg if data is not available) Total.	P-SAC [3], F-SAC [4]

Safety: Tables					
No.	Population	IDSL / Example Shell	Title	Programming Notes	Deliverable [Priority]
3.0015	All Treated	AE5B	Summary of Adverse Events by Preferred Term and Maximum Grade	Report for: Part 1, Part 2, and combined Part 1 and Part 2; Summarize by: dose level (Refer to Section 5.1 for ordering of dose level and omit 1.92 mg/kg if data is not available), Total.; Do not include SOC	HDL [2], P-SAC [3], F-SAC [4]
3.0016	All Treated	AE5B	Summary of Adverse Events Related to Study Treatment by Maximum Grade	Report for: Part 1, Part 2, and combined Part 1 and Part 2; Summarize by: dose level (Refer to Section 5.1 for ordering of dose level and omit 1.92 mg/kg if data is not available), Total.; Do not include SOC	P-SAC [3], F-SAC [4]
3.0017	All Treated	AE5B	Summary of Adverse Events by Maximum Grades 3-5	Report for: Part 1, Part 2, and combined Part 1 and Part 2; Summarize by: dose level (Refer to Section 5.1 for ordering of dose level and omit 1.92 mg/kg if data is not available), Include Any Grade column with footnote as defined as "The 'Any Grade' column includes events with Grade 1-5 or missing grade."; Exclude Grade 1, Grade 2, Unknown, and Total column; Do not include SOC	P-SAC [3], F-SAC [4]
3.0018	All Treated	AE3	Summary of Adverse Events Leading to Dose Reductions by Preferred Term	Report for: Part 1, Part 2, and combined Part 1 and Part 2; Summarize by: dose level (Refer to Section 5.1 for ordering of dose level and omit 1.92 mg/kg if data is not available), Total.	P-SAC [3], F-SAC [4]

Safety: Tables					
No.	Population	IDSL / Example Shell	Title	Programming Notes	Deliverable [Priority]
3.0019	All Treated	AE3	Summary of Adverse Events Leading to Drug Interruptions by Preferred Term	Report for: Part 1, Part 2, and combined Part 1 and Part 2; Summarize by: dose level (Refer to Section 5.1 for ordering of dose level and omit 1.92 mg/kg if data is not available) Total.	P-SAC [3], F-SAC [4]

Safety: Tables					
No.	Population	IDSL / Example Shell	Title	Programming Notes	Deliverable [Priority]
Immune-Related Adverse Events: Pembrolizumab					
3.0020	All Treated	AE5B	Summary of All Immune-Related Adverse Events by System Organ Class and Preferred Term and Maximum Grade	Report for: Part 1, Part 2, and combined Part 1 and Part 2; Summarize by: dose level (Refer to Section 5.1 for ordering of dose level and omit 1.92 mg/kg if data is not available) Total.	P-SAC [3], F-SAC [4]

Safety: Tables					
No.	Population	IDSL / Example Shell	Title	Programming Notes	Deliverable [Priority]
3.0021	All Treated	AE13	Immune-Related Adverse Events Overview	
Report for: Part 1, Part 2, and combined Part 1 and Part 2; Summarize by: dose level (Refer to Section 5.1 for ordering of dose level and omit 1.92 mg/kg if data is not available) Total. Refer to mid205678 (primary_01) Table 3.0010 for guidance; Include the following Any AE subcategory, Replace "AE" with "irAE" and "SAE" with "serious irAE" Include the following subcategories:
 
 • irAEs leading to dose interruption and/or dose reduction; • irAEs related to study treatment and lead to permanent discontinuation of study treatment • Grade 2 irAEs • Grade 3 or 4 irAEs related to study treatment 	P-SAC [3], F-SAC [4]
3.0022	All Treated	AE3	Summary of Immune-Related Adverse Events Leading to Drug Interruptions by Preferred Term	Report for: Part 1, Part 2, and combined Part 1 and Part 2; Summarize by: dose level (Refer to Section 5.1 for ordering of dose level and omit 1.92 mg/kg if data is not available) Total.	P-SAC [3], F-SAC [4]

Safety: Tables					
No.	Population	IDSL / Example Shell	Title	Programming Notes	Deliverable [Priority]
Adverse Events of Special Interest: belantamab mafodotin					
3.0023	All Treated	ESI1	Summary of Characteristics of Corneal Events (GSK scale)	Report for: Part 1, Part 2, and combined Part 1 and Part 2; Summarize by: dose level (Refer to Section 5.1 for ordering of dose level and omit 1.92 mg/kg if data is not available) Total. Summary based on both all subjects and subjects with events.	HDL [2], P-SAC [3], F-SAC [4]
3.0024	All Treated	ESI1	Summary of Characteristics of Eye Disorders (CTCAE)	Report for: Part 1, Part 2, and combined Part 1 and Part 2; Summarize by: dose level (Refer to Section 5.1 for ordering of dose level and omit 1.92 mg/kg if data is not available) Total. Summary based on both all subjects and subjects with events.	P-SAC [3], F-SAC [4]

Safety: Tables					
No.	Population	IDSL / Example Shell	Title	Programming Notes	Deliverable [Priority]
3.0025	All Evaluable	ESI1	Summary of Characteristics of Eye Disorders (CTCAE)	
Report for: futility interim analyses for part 2 participants and part 1 participants who initially received the RP2D (Refer to Section 5.1 for ordering of dose level)
 
Add the following footnote: A subject is evaluable for interim analysis if the subject fulfils the criteria for 'All Treated' population with adequate baseline assessment and measurable disease meet at least one of the following criteria: if the planned assessment is every 3 weeks and at least three assessments are required, the time from the first dose to the time of data cut-off is more than 66 days, OR had an unconfirmed response of PR/CR or better, progressed, OR died, OR discontinued treatment due to other reasons.
	IA [1]
3.0026	All Treated	ESI1	Summary of Characteristics of Thrombocytopenia	Report for: Part 1, Part 2, and combined Part 1 and Part 2; Summarize by: dose level (Refer to Section 5.1 for ordering of dose level and omit 1.92 mg/kg if data is not available) Total. Summary based on both all subjects and subjects with events.	HDL [2], P-SAC [3], F-SAC [4]

Safety: Tables					
No.	Population	IDSL / Example Shell	Title	Programming Notes	Deliverable [Priority]
3.0027	All Evaluable	ESI1	Summary of Characteristics of Thrombocytopenia	
Report for: futility interim analyses for part 2 participants and part 1 participants who initially received the RP2D (Refer to Section 5.1 for ordering of dose level)
 
Add the following footnote: A subject is evaluable for interim analysis if the subject fulfils the criteria for 'All Treated' population with adequate baseline assessment and measurable disease meet at least one of the following criteria: if the planned assessment is every 3 weeks and at least three assessments are required, the time from the first dose to the time of data cut-off is more than 66 days, OR had an unconfirmed response of PR/CR or better, progressed, OR died, OR discontinued treatment due to other reasons.
	IA [1]
3.0028	All Treated	ESI1	Summary of Characteristics of Infusion Related Reactions	Report for: Part 1, Part 2, and combined Part 1 and Part 2; Summarize by: dose level (Refer to Section 5.1 for ordering of dose level and omit 1.92 mg/kg if data is not available) Total. Summary based on both all subjects and subjects with events.	HDL [2], P-SAC [3], F-SAC [4]

Safety: Tables					
No.	Population	IDSL / Example Shell	Title	Programming Notes	Deliverable [Priority]
3.0029	All Treated	See programming notes	Summary of Keratopathy Events (CTCAE) Characteristics II	Report for: Part 1, Part 2, and combined Part 1 and Part 2; Summarize by: dose level (Refer to Section 5.1 for ordering of dose level and omit 1.92 mg/kg if data is not available), Total; Refer to mid205678 (primary_01) Table 3.0200 for guidance.	P-SAC [3], F-SAC [4]
3.0030	All Treated	ESI2a	Summary of Onset and Duration of the First Occurrence of Grade 2 or Above Corneal Events (GSK scale)	Report for: Part 1, Part 2, and combined Part 1 and Part 2; Summarize by: dose level (Refer to Section 5.1 for ordering of dose level and omit 1.92 mg/kg if data is not available), Total; Time of onset: 1-21, 22-42, 43-63, >63. Duration till resolution: 1-21, 22-42, >42.	P-SAC [3], F-SAC [4]
3.0031	All Treated	ESI2a	Summary of Onset and Duration of the First Occurrence of Eye Disorders (CTCAE)	Report for: Part 1, Part 2, and combined Part 1 and Part 2; Summarize by: dose level (Refer to Section 5.1 for ordering of dose level and omit 1.92 mg/kg if data is not available), Total; Time of onset: 1-21, 22-42, 43-63, >63. Duration till resolution: 1-21, 22-42, >42.	P-SAC [3], F-SAC [4]
3.0032	All Treated	ESI2a	Summary of Onset and Duration of the First Occurrence of Thrombocytopenia	Report for: Part 1, Part 2, and combined Part 1 and Part 2; Summarize by: dose level (Refer to Section 5.1 for ordering of dose level and omit 1.92 mg/kg if data is not available), Total; Time of onset: 1-21, 22-42, 43-63, >63. Duration till resolution: 1-21, 22-42, >42.	P-SAC [3], F-SAC [4]

Safety: Tables					
No.	Population	IDSL / Example Shell	Title	Programming Notes	Deliverable [Priority]
3.0033	All Treated	ESI2a	Summary of Onset and Duration of the First Occurrence of Infusion Related Reactions	Report for: Part 1, Part 2, and combined Part 1 and Part 2; Summarize by: dose level (Refer to Section 5.1 for ordering of dose level and omit 1.92 mg/kg if data is not available), Total; Time of onset: 1-21, 22-42, 43-63, >63. Duration till resolution: 1-21, 22-42, >42.	P-SAC [3], F-SAC [4]
3.0034	All Treated	See programming notes	Summary of Corneal Events (GSK scale) by Grade and Visit	Report for: Part 1, Part 2, and combined Part 1 and Part 2; Summarize by: dose level (Refer to Section 5.1 for ordering of dose level and omit 1.92 mg/kg if data is not available) Total. Include Worst-case baseline visit.; Refer to mid205678 (primary_01) Table 3.0340 for guidance.	P-SAC [3], F-SAC [4]
3.0035	All Treated	AE5B	Summary of Eye Disorders (CTCAE) by Preferred Term and Maximum Grade	Report for: Part 1, Part 2, and combined Part 1 and Part 2; Summarize by: dose level (Refer to Section 5.1 for ordering of dose level and omit 1.92 mg/kg if data is not available) Total; Do not include SOC	P-SAC [3], F-SAC [4]
3.0036	All Treated	AE5B	Summary of Thrombocytopenia by Preferred Term and Maximum Grade	Report for: Part 1, Part 2, and combined Part 1 and Part 2; Summarize by: dose level (Refer to Section 5.1 for ordering of dose level and omit 1.92 mg/kg if data is not available) Total.; Do not include SOC	P-SAC [3], F-SAC [4]

Safety: Tables					
No.	Population	IDSL / Example Shell	Title	Programming Notes	Deliverable [Priority]
3.0037	All Treated	AE5B	Summary of Infusion Related Reactions by Preferred Term and Maximum Grade	Report for: Part 1, Part 2, and combined Part 1 and Part 2; Summarize by: dose level (Refer to Section 5.1 for ordering of dose level and omit 1.92 mg/kg if data is not available) Total.; Do not include SOC	P-SAC [3], F-SAC [4]
3.0038	All Treated	See programming notes	Summary of Time to Re-initiation of Study Treatment Post First Treatment Interruption/Delay due to Corneal Events (GSK Scale)	Report for: Part 1, Part 2, and combined Part 1 and Part 2; Summarize by: dose level (Refer to Section 5.1 for ordering of dose level and omit 1.92 mg/kg if data is not available) Total. Refer to mid205678 (primary_01) Table 3.0430 for guidance.	P-SAC [3], F-SAC [4]
3.0039	All Treated	See programming notes	Summary of Action Taken with Study Treatment for Corneal Events (GSK Scale) by Visit and Grade	Report for: Part 1, Part 2, and combined Part 1 and Part 2; ; Summarize by: dose level (Refer to Section 5.1 for ordering of dose level and omit 1.92 mg/kg if data is not available) Total. Refer to mid205678 (primary_01) Table 3.0380 for guidance.	P-SAC [3], F-SAC [4]

Safety: Tables					
No.	Population	IDSL / Example Shell	Title	Programming Notes	Deliverable [Priority]
Identified Risks: belantamab mafodotin					
3.0040	All Treated	ESI1	Summary of Characteristics of Neutropenia	Report for: Part 1, Part 2, and combined Part 1 and Part 2; Summarize by: dose level (Refer to Section 5.1 for ordering of dose level and omit 1.92 mg/kg if data is not available), Total; Summary based on both all subjects and subjects with events.	P-SAC [3], F-SAC [4]
3.0041	All Treated	ESI2a	Summary of Onset and Duration of the First Occurrence of Neutropenia	Report for: Part 1, Part 2, and combined Part 1 and Part 2; Summarize by: dose level (Refer to Section 5.1 for ordering of dose level and omit 1.92 mg/kg if data is not available), Total; Time of onset: 1-21, 22-42, 43-63, >63. Duration till resolution: 1-21, 22-42, >42.	P-SAC [3], F-SAC [4]
3.0042	All Treated	AE5B	Summary of Neutropenia by Preferred Term and Maximum Grade	Report for: Part 1 and Part 2; Summarize by: dose level (Refer to Section 5.1 for ordering of dose level and omit 1.92 mg/kg if data is not available), Total.; Do not include SOC	P-SAC [3], F-SAC [4]

Safety: Tables					
No.	Population	IDSL / Example Shell	Title	Programming Notes	Deliverable [Priority]
Serious and Other Significant Adverse Events					
3.0043	All Treated	AE16	Summary of Serious Adverse Events by System Organ Class and Preferred Term (Number of Subjects and Occurrences)	Report for: Part 1, Part 2, and combined Part 1 and Part 2; Summarize by: dose level (Refer to Section 5.1 for ordering of dose level and omit 1.92 mg/kg if data is not available) Total.	P-SAC [3], F-SAC [4]
3.0044	All Treated	AE3	Summary of Adverse Events Leading to Permanent Discontinuation of Study Treatment by Overall Frequency	Report for: Part 1, Part 2, and combined Part 1 and Part 2; Summarize by: dose level (Refer to Section 5.1 for ordering of dose level and omit 1.92 mg/kg if data is not available) Total.	P-SAC [3], F-SAC [4]
3.0045	All Treated	AE3	Summary of Serious Adverse Events	Report for: Part 1, Part 2, and combined Part 1 and Part 2; Summarize by: dose level (Refer to Section 5.1 for ordering of dose level and omit 1.92 mg/kg if data is not available) Total.	P-SAC [3], F-SAC [4]
3.0046	All Treated	AE3	Summary of Serious Drug-Related Adverse Events by Overall Frequency	Report for: Part 1, Part 2, and combined Part 1 and Part 2; Summarize by: dose level (Refer to Section 5.1 for ordering of dose level and omit 1.92 mg/kg if data is not available) Total.	P-SAC [3], F-SAC [4]
3.0047	All Treated	AE3	Summary of Fatal Adverse Events	Report for: Part 1, Part 2, and combined Part 1 and Part 2; Summarize by: dose level (Refer to Section 5.1 for ordering of dose level and omit 1.92 mg/kg if data is not available) Total.	P-SAC [3], F-SAC [4]

Safety: Tables					
No.	Population	IDSL / Example Shell	Title	Programming Notes	Deliverable [Priority]
3.0048	COVID-19	AE3	Summary of COVID-19 Adverse Events Leading to Permanent Discontinuation of Study Treatment by Overall Frequency	Report for: Part 1, Part 2, and combined Part 1 and Part 2; Summarize by: dose level (Refer to Section 5.1 for ordering of dose level and omit 1.92 mg/kg if data is not available), Total. only if greater than 5 participants with COVID-19 infection	P-SAC [3], F-SAC [4]
Serious and Other Significant Immune-related Adverse Events: pembrolizumab					
3.0049	All Treated	AE3	Summary of Fatal Immune-Related Adverse Events	Report for: Part 1, Part 2, and combined Part 1 and Part 2; Summarize by: dose level (Refer to Section 5.1 for ordering of dose level and omit 1.92 mg/kg if data is not available) Total.	P-SAC [3], F-SAC [4]

Safety: Tables					
No.	Population	IDSL / Example Shell	Title	Programming Notes	Deliverable [Priority]
Ocular Findings					
3.0050	All Treated	See programming notes	Shift in Corneal Epithelium Exam Results from Baseline to Worst Post-Baseline for Other Exams	
Report for: Part 1, Part 2, and combined Part 1 and Part 2; Summarize by: dose level (Refer to Section 5.1 for ordering of dose level and omit 1.92 mg/kg if data is not available) Total.; Refer to mid205678 (primary_01) Table 3.0852 for guidance.
 
Include the following corneal exams: Microcyst without Edema, Subepithelial Haze, Corneal Neovascularization, Epithelial Microcystic Edema, Corneal Ulcer
 
Add the following footnote: Note: Baseline percentage is based on N. Percentage for worst post-Baseline value is based on Baseline n.
	P-SAC [3], F-SAC [4]
3.0051	All Treated	See programming notes	Shift in Corneal Epithelium Exam Results from Baseline to Worst Post-Baseline for Corneal Epithelium	
Report for: Part 1, Part 2, and combined Part 1 and Part 2; Summarize by: dose level (Refer to Section 5.1 for ordering of dose level and omit 1.92 mg/kg if data is not available) Total.; Refer to mid205678 (primary_01) Table 3.0850 for guidance.
 
Include the following corneal exams: Corneal Epithelium
 
Add the following footnote: Note: Baseline percentage is based on N. Percentage for worst post-Baseline value is based on Baseline n.
	P-SAC [3], F-SAC [4]

Safety: Tables					
No.	Population	IDSL / Example Shell	Title	Programming Notes	Deliverable [Priority]
3.0052	All Treated	See programming notes	Summary of Characteristics II of Worsening in Best Corrected Visual Acuity (BCVA) Score (logMAR Score)	
Report for: Part 1, Part 2, and combined Part 1 and Part 2; Summarize by: dose level (Refer to Section 5.1 for ordering of dose level and omit 1.92 mg/kg if data is not available) Total.; Refer to mid205678 (primary_07) Table 3.12060 for guidance.
 
Add the following footnotes:
 
[1] Duration is the time from onset of any visual acuity event (change from baseline logMAR score ≥ 0.3 in either eye) until the event is resolved (change from baseline logMAR score < 0.3 in both eyes). It requires at least a one day gap between the resolution of all events from first occurrence to the onset of second occurrence. [2] Snellen acuity response of "no equivalent value" will be set to a logMAR value of 1000 to indicate a worsening in result if there is a corresponding Non-Snellen acuity response. [3] If a subject has both a Snellen acuity and Non-Snellen acuity recorded at a visit, the Snellen acuity value will be selected. [4] The end of treatment exposure is defined as last infusion date +20 days.
	P-SAC [3], F-SAC [4]

Safety: Tables					
No.	Population	IDSL / Example Shell	Title	Programming Notes	Deliverable [Priority]
3.0053	All Treated	See programming notes	Summary of Findings for Punctate Keratopathy	
Report for: Part 1, Part 2, and combined Part 1 and Part 2; Summarize by dose level (refer to Section 5.1 for ordering of dose level and omit 1.92 mg/kg if data is not available; Total; Refer to mid205678 (internal_05) Table 3.0860 for guidance.
 
Add the following footnote:
 
Note: n reflects the number of eyes with punctate keratopathy worse than baseline at any post-baseline ocular exam.
	P-SAC [3], F-SAC [4]
